#### 7.9.2. Inter-Reader Reliability

For the primary analysis of the primary endpoint the inter-reader reliability will be estimated using the multiple-reader generalized kappa statistic developed by Fleiss.

$$Kappa = \frac{\bar{p} - \bar{p}_e}{1 - \bar{p}_e}$$

Variance: 
$$\frac{2}{NK(K-1)} \frac{\sum_{j=1}^{R} p_j^2 + (\sum_{j=1}^{R} p_j^2)^2 - 2\sum_{j=1}^{R} p_j^3}{(1 - \sum_{j=1}^{R} p_j^2)^2}$$

Where

$$p_j = \frac{1}{NK} \sum_{i=1}^{N} n_{ij}$$

$$p_i = \frac{\sum_{j=1}^{R} n_{ij} (n_{ij} - 1)/2}{K(K-1)/2}$$

$$\bar{p} = \frac{\sum_{i=1}^{N} p_i}{N}$$
 (overall agreement)

$$\bar{p}_e = \sum_{j=1}^R p_j^2$$
 (expected chance agreement)

The generalized Kappa statistic and a 95% confidence interval will be computed.

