## 4.3. Sample Size

The primary analysis in Cohort A will test the co-primary endpoints of sensitivity and specificity of F-DCFPyL PET imaging relative to histopathology for the evaluable set of subjects in Cohort A with metastatic disease. For each co-primary endpoint, there will be three independent imaging readers. At least two of the three readers must reject the null hypothesis for specificity to be deemed a success. If specificity is a success, then the same two readers need to reject the null hypothesis for sensitivity leading to overall success of the primary endpoint. The null hypotheses will be tested in the following order:

- 1. Specificity of F-DCFPyL PET imaging relative to histopathology in Cohort A  $H_0$ :  $\pi_{Sp} = 0.80$  versus  $H_1$ :  $\pi_{Sp} \neq 0.80$
- 2. Sensitivity of F-DCFPyL PET/CT imaging relative to histopathology in Cohort A  $H_{01}$ :  $\pi_{Se} = 0.40$  versus  $H_{11}$ :  $\pi_{Se} \neq 0.40$

where  $\pi_{Se}$  is the true sensitivity and  $\pi_{Sp}$  is the true specificity of F-DCFPyL PET imaging.

A total of 262 subjects from Cohort A will provide 80% power to reject the null hypothesis about sensitivity at the 5% significance level if the true sensitivity is at least 60% and at least 80% power to reject the null hypothesis about specificity at the 5% significance level if the true specificity is at least 87.8%. These calculations are based on the following assumptions:

• the probability of a positive histopathology sample in Cohort A is 20%,

The sample size is based on the normal approximation to the binomial distribution without a continuity correction.

$$n \ge \left\{ \frac{z_{\alpha/2} \sqrt{P_0(1 - P_0)} + z_{\beta} \sqrt{P_1(1 - P_1)}}{P_1 - P_0} \right\}^2$$

where P0 are P1 are values of sensitivity under the null and alternative hypotheses, respectively. After adjusting sensitivity and specificity separately by their corresponding prevalence values, a total in 236 subjects are needed. Assuming a 10% drop out or non-evaluable rate increases the required number of subjects in Cohort A to 262.

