## 7.6. Analysis of the Primary Efficacy Endpoint

### 7.6.1. Primary Efficacy Analysis of Primary Endpoints

The primary analysis for subjects in Cohort A will be addressed by computing point estimates and 95% two-sided confidence intervals (CIs) for specificity first and if the null hypothesis is rejected for specificity then sensitivity will be tested next. Both outcomes are assessed on the subject level (one overall outcome per subject) in the *evaluable set*. If the *per protocol* set exists, then this analysis will be performed on the *per protocol* set as a supplemental analysis. The normal approximation to the binomial distribution is planned assuming the assumptions have been met (See Section 7.2). Sensitivity and specificity will be computed for each of three central imaging core lab independent PET/CT readers.

The null hypothesis for specificity will be rejected if the lower limit of the 95% CI exceeds 80% for at least two of the three independent central PET/CT readers. If statistical significance is achieved for specificity where the null hypothesis is rejected, then sensitivity will be tested where the null hypothesis will be rejected if the lower limit of the 95% CI exceeds 40% for the same two readers who rejected the null hypothesis for specificity.

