## 7.9. Reader Reliability

There are four imaging readers who were trained to perform our central reads used in much of the analyses. Only three of these readers will perform these reads with the fourth reader as an alternative if needed. Variability of these readers regarding the primary endpoint for the evaluable set will be tested as described below. The following is assumed:

Ni=total number of subjects with the primary endpoint in the evaluable set (i=1, 2,...N)

K=number of readers (3)

 $R_i$ = number of responses (i=1,2)

nij=number of times subject i is in response group j

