#### 7.9.1. Intra-Reader Reliability

Prior to reading any images, a random subset of 30 PyL images will be randomly selected by the Imaging vendor. Once the reads start, this subset will be re-introduced to each reader no sooner than 3 weeks after the original read. They will be read under identical conditions as the original read (same criteria evaluation, same analysis reporting, same analysis platform). The rate of agreement between the original reads and the re-reads for the primary endpoint in this subset will be compared using the intra-rater variability defined from Cohen's Kappa. This calculation will be performed for each reader separately.

Cohen's Kappa = 
$$\frac{p_{a-}p_e}{(1-p_e)}$$
where  $p_a = \sum_{j=1}^R \frac{n_{jj}}{n}$ 

$$p_e = \sum_{j=1}^R \frac{n_{j+}}{n} \frac{n_{+j}}{n}$$

The standard error of Kappa  $\sigma_k\,\underline{w}ill$  be calculated as:

$$\sigma_{k} = \sqrt{\frac{P_{a}(1-P_{a})}{N(1-P_{e})^{2}}}$$

It is assumed that the concordance rate between time points for each reader will be at minimum of 93% with a Kappa of 86%. This would yield a 95% confidence interval of (0.68, 1) for a sample of 30 subjects.

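### The only variance the SAP gives for the inter-reader kappa is the kappa = 0 variance; with three readers and two responses it is always 1/(3N), so the 95% CI width ignores the observed agreement

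*SAP*

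**What the plan says.** SAP 7.9 sets up reader reliability for the primary endpoint with K = 3 readers and two possible responses. It defines N as the "total number of subjects with the primary endpoint in the evaluable set". SAP 7.9.2 names the Fleiss multiple-reader kappa and prints one variance:

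`Var = 2/(N·K·(K−1)) × [Σp_j² + (Σp_j²)² − 2Σp_j³] / (1 − Σp_j²)²`

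Here p_j is the overall proportion of reads in category j. The section defines the observed agreement, which enters kappa itself but not this variance. It closes with "The generalized Kappa statistic and a 95% confidence interval will be computed". No bootstrap, alternative standard error or other interval method is given for the inter-reader kappa.

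SAP 7.9.1 treats the intra-reader kappa differently: the expression under "The standard error of Kappa" there is built from the observed agreement P_a. Both reliability results go to Table 14.2.3-14.

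**The concern.** An interval around an estimated kappa should reflect the sampling variability at that level of agreement. A variance that depends only on how often readers call a scan positive cannot do this. It suits a test of no agreement beyond chance, but not an interval around a kappa expected to be well above zero.

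If it is used for the interval, two data sets of equal size, one with moderate and one with excellent agreement, get intervals of identical width. What is at stake is how well readers of the study report can judge the precision of the reader-agreement result. No efficacy conclusion depends on it.

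**Working it through.** **The plan's own figures.** The documents state no number for the inter-reader interval. The nearest is the intra-reader one in SAP 7.9.1, with concordance 0.93, kappa 0.86 and 30 subjects:

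- Pe = (0.93 − 0.86)/(1 − 0.86) = 0.50
- SE = √(0.93 × 0.07/(30 × 0.50²)) = 0.0932
- 0.86 ± 1.96 × 0.0932 = 0.677 to 1.043, which the SAP gives as (0.68, 1). It reproduces.

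For N, SAP 4.3 says "a total in 236 subjects are needed". Its formula with 0.40 against 0.60 and 80% power gives 47.09 positives; 47.09/0.20 = 235.5, so 236 reproduces.

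**Algebra.** Let p be the proportion of positive reads and q = 1 − p.

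- Σp_j² = 1 − 2pq and Σp_j³ = 1 − 3pq.
- Numerator: (1 − 2pq) + (1 − 2pq)² − 2(1 − 3pq) = 4p²q².
- Denominator: (1 − (1 − 2pq))² = 4p²q².
- The ratio is 1, so Var = 2/(N × 3 × 2) = 1/(3N).

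The only exception is 0/0, when every read falls in one category. At N = 236, Var = 1/708 = 0.0014124, SE = 0.0376 and the half-width is 1.96 × 0.0376 = 0.074. It is 0.080 at N = 200 and 0.070 at N = 262.

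**Worked data.** These are invented, with N = 236 and 19–20% positive reads.

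| Subjects with 0/1/2/3 positive reads | Kappa | CI from the SAP variance | Jackknife SE | Jackknife CI |
|---|---|---|---|---|
| 161/34/24/17 | 0.463 | 0.389–0.537 | 0.0548 | 0.356–0.570 |
| 184/6/4/42 | 0.911 | 0.837–0.985 | 0.0278 | 0.856–0.966 |

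For the first row, observed agreement is (161 + 17 + 58/3)/236 = 0.836. The positive rate is 133/708 = 0.188, so chance agreement is 0.695 and kappa = (0.836 − 0.695)/(1 − 0.695), which is 0.463 before rounding.

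**Simulated coverage of the fixed-width interval.** N = 236, three exchangeable readers, 10,000 replicates per setting. The range is over mixture, beta-binomial and latent-normal agreement models.

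| True kappa | Coverage, 20% positive reads |
|---|---|
| 0 (two models) | 95–96% |
| 0.15 | 84.0–87.9% |
| 0.30 | 79.2–83.9% |
| 0.45 | 77.9–82.5% |
| 0.65 | 84.1–86.7% |
| 0.80 | 92.6–93.7% |
| 0.85 | 95.6–96.4% |
| 0.90 | 98.6–98.9% |

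At kappa 0 the simulated SD is 0.037–0.038 against the formula's 0.0376, which confirms that this is the null variance.

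The read rate matters. For kappa 0.15–0.65, coverage is 62–80% at 10% positive, 80–89% at 21.8%, 86–92% at 29.8% and 91–95% at 50%.

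**The SAP 4.3 inputs.** With prevalence 20%, sensitivity 60%, specificity 87.8% and reads assumed independent given the true status:

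- Positive rate = 0.2 × 0.6 + 0.8 × 0.122 = 0.2176
- Kappa = 0.2 × 0.8 × (0.6 − 0.122)²/(0.2176 × 0.7824) = 0.215
- Simulated SD is 0.050 and coverage is about 85–86%. A jackknife interval has half-width 0.099 and covers 94.5%.

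**The case against.** The SAP never says that the interval uses the printed variance, and SAP 7.9 says reader variability will be tested, for which a kappa = 0 variance is correct. On that reading the interval method is unspecified rather than wrong. This is fair as far as it goes. But no other standard error is offered, so using this one is the natural reading, and either reading needs the same added sentence.

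The size of the error rests on assumed values. The only kappa the plan states is 0.86, for intra-reader agreement. At that value, with 20–21.8% positive reads, the correct half-width is about 0.066–0.069 against 0.074, and coverage is about 97%. The kappa of 0.215 needs reader errors to be independent given the truth. Readers of the same scan probably share errors, and a within-truth error correlation of 0.3, 0.5, 0.7 or 0.8 gives kappa 0.45, 0.61, 0.76 or 0.84. The 10% read rate appears nowhere in the documents. All of this stands and limits the likely size, but coverage is still 78–87% at kappa 0.45–0.65 with 20% positive reads, and the constant width needs no such assumption.

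Intervals from this variance also pass 1 once kappa exceeds 0.926 (1 − 0.074). That is incidental, because the 7.9.1 interval does so too and is truncated.

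Finally, no decision uses kappa. Reader agreement is not an objective or endpoint, its table sits in the exploratory block, and SAP 7.6.1 rejects the sensitivity null hypothesis "if the lower limit of the 95% CI exceeds 40% for the same two readers who rejected the null hypothesis for specificity", without reference to kappa. This stands and sets the severity.

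**Conclusion.** The concern holds, as a minor point. That the variance equals 1/(3N) is exact for three readers and two responses and does not depend on the data. Used for the interval, it gives a fixed half-width of 0.074 at N = 236. Near the read rate implied by the plan (about 20–22% positive), that is too narrow at low to moderate kappa, about right at 0.80–0.85, and too wide near 0.90.

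The coverage figures rest on assumed inter-reader kappas, read rates and agreement models, for which the ranges are shown. The conclusion also rests on reading the printed variance as the one meant for the interval. Kappa estimates, the primary analysis and the success rule are unaffected.

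**What to change.** Replace the last sentence of SAP 7.9.2 with wording such as:

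> The generalized Kappa statistic will be reported with a 95% confidence interval from a subject-level jackknife standard error. The variance shown above will be used only for a test of kappa = 0.

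A subject-level bootstrap or the large-sample non-null variance of the generalized kappa would also serve.

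The cost is one SAP sentence and a few lines of code. Near 20% positive reads the interval becomes wider below a kappa of about 0.8 (half-width 0.106–0.117 instead of 0.074 at 0.45) and narrower at high kappa (0.057–0.058 at 0.90). The jackknife is itself slightly below nominal in places: 93–95% coverage at 20–21.8% positive reads and 91–95% at 10%.

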#### 8. SAFETY AND TOLERABILITY

All safety data will be summarized by cohort.

# 8.1. Adverse Event Preferred Term and System Organ Class Summary Tables

An overall summary of frequency and percentage of treatment-emergent adverse events (TEAEs), most frequent (>5%) overall TEAEs, serious TEAEs, severe TEAEs (grade  $\geq$  3), TEAEs by grade, and treatment-related TEAEs will be presented by cohort and overall using the safety set.

#### 8.1.1. Summaries of Adverse Event Incidence Rates for All Subjects

Treatment-emergent adverse events will be summarized by SOC and PT using the frequency and percentage of subjects experiencing any adverse event, experiencing each SOC and experiencing each PT within each SOC, using the safety set. The number of occurrences of each adverse event will be included.

Treatment-emergent adverse events will be summarized by severity and for subjects who report adverse events with severity grades 3 or higher. The most severe occurrence of each event will be summarized by SOC and PT using the frequency and percentage of subjects experiencing any adverse event, experiencing each SOC and experiencing each PT within each SOC by cohort and overall, using the safety analysis set.

Treatment-emergent adverse events will be summarized by relationship to study drug. The most closely related occurrence of each event will be summarized by SOC and PT using the frequency and percentage of subjects experiencing any adverse event, experiencing each SOC and experiencing each PT within each SOC by cohort and overall, using the safety analysis set.

# 8.1.2. Summaries of Adverse Incidence Rates for Serious Adverse Events (SAE), Adverse Event Discontinuations, and Death

The overall summary table includes incidences of serious adverse events, adverse events that led to discontinuation and deaths.

Separate listings for serious adverse events, adverse events that led to discontinuation and deaths will be created.

## 8.2. Exposure to Study Drug

Exposure to study drug will be summarized using summary statistics for volume administered, location of injection, correction factor at pre and post dose, the decay corrected dose in mCi and MBq at time of administration, and any dose change due to an AE for the safety set.

#### **8.3.** Concomitant and Other Medications

Concomitant medications will be summarized by ATC4 class and generic term using frequencies and percentages for the safety analysis set.

### **8.4.** Routine Laboratory Data

Summary statistics for observed and change from baseline values of each laboratory analyte will be presented by visit for the safety set. Labs will include hematology and chemistry. A shift table will also be presented showing the shift in values from Baseline to follow up (below LLN, within LLN and ULN, above ULN, and missing). The following parameters will be created and summarized also:

Leukocytes = sum of Basophils, Eosinophils, Lymphocytes, Monocytes, and Neutrophils

Basophils/leukocytes = (Basophils/leukocytes)\*100

Eosinophils/leukocytes = (Eosinophils /leukocytes)\*100

Lymphocytes/leukocytes = (Lymphocytes /leukocytes)\*100

Monocytes/leukocytes = (Monocytes /leukocytes)\*100

Neutrophils/leukocytes = (Neutrophils /leukocytes)\*100

## 8.5. Vital Signs

Summary statistics for observed and change from baseline values of each vital sign (systolic and diastolic blood pressures, heart rate, respiratory rate, and temperature) will be presented by visit and cohort for the safety set.

#### **8.6.** ECG

Summary statistics for observed and change from baseline values of each ECG parameter will be presented by visit and cohort using the safety set. For QT interval, adjudicated QTc-Bazett and adjudicated QTc-Fidericia, the following groups will be summarized at Baseline and the pre-imaging visit: values above 450, above 480 and above 500. For these same parameters the following will be summarized at the pre-imaging time point only: Increase 31-50, increase >60, decrease 31-60, and decrease >60.

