11.1.4. Electrocardiogram (ECG)

A 12-lead electrocardiogram (ECG) will be taken at two intervals on the day of dosing, including prior to dosing and prior to imaging. Please refer to the ECG Procedure Manual for acquisition and transmittal details. The onsite Investigator has the responsibility to evaluate the ECG for the assessment of subject safety. Adverse events will be reported in the CRF.

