12.5.3.4. ECG

Observed values and changes will be tabulated for each visit using summary statistics. Shift tables comparing pre- to post-dosing categorical ECG values will be presented using the *safety set*.

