# 10. PLANNED TREATMENT SAP CHANGES THAT DIFFER FROM THE PROTOCOL

- Screened population renamed to consented population as the definition states all subjects need to provide consent and not screening data.
- The Evaluable set was updated to state that subjects in Cohort A are required to have a prostatectomy and lymphadenectomy.
- The Change in Planned Protocol Procedure Set was added as a subject population to capture the subjects who had a change in the planned protocol procedure.
- The PK Evaluable set was divided into two groups: The PK Blood Set and the PK Urine set, as a subject could meet the criteria for one of these, but not the other.
- 'PPV of 18F-DCFPyL PET/CT imaging in subjects with corresponding histopathology that is outside the planned protocol surgical template or biopsy site' was updated to 'PPV of 18F-DCFPyL PET/CT imaging in subjects with corresponding histopathology for subjects who had a change in planned treatment per Cohort assignment'. Subjects may undergo a planned protocol procedure defined per the other cohort.
- The number of lesions per subject plotted against PSA and baseline testosterone for each of the 3 central imaging core lab readers will no longer be performed.
- SUVmax, SUVpeak, SUVr will no longer be summarized by subgroups: Previous radiation therapy (yes/no), Previous hormonal therapy (yes/no), or Previous chemotherapy (yes/no). Most subjects will be from cohort B only.
- Sensitivity will no longer be summarized by previous radiation therapy, previous hormonal therapy or previous chemotherapy. Since it is no longer the primary endpoint and it's not appropriate to combine cohorts for this analysis, it is no longer of interest.
- The following was added for PK: Additional blood concentration time data will be fitted into a two-compartmental model to calculate T1/2-alpha and T1/2-beta. For % of injected dose recovered per each urine collection interval per subject will be used to calculate Tmax, Rate max, Rate last, T1/2elim, and cumulative urine recovery if feasible.

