14.2.3-10	PPV and Positive Imaging from any tissue compared to histology for both Cohorts Combined -Change in Management Set		
14.2.3-11	Summary of Imaging Results-Safety Set		
14.2.3-12	Summary of Histology Results- Safety Set		
14.2.3-13	Summary of Procedures- Safety Set		
14.2.3-14	Inter-Reader and Intra-Reader Variability for Cohort A- Evaluable Set		
14.2.4: Ef	14.2.4: Efficacy- Per Protocol Set		
14.2.4-1	Specificity and Sensitivity of the Pelvic Lymph Nodes for the Subjects in Cohort A- Per-Protocol Set		
14.3.1: Ad	lverse Events- Safety Set		
14.3.1-1	Summary of Treatment Emergent Adverse Events, Overall and by Cohort -Safety Set		
14.3.1-2	Most Frequent (>5% Overall) Treatment Emergent Adverse Events, Overall and by Cohort-Safety Set		
14.3.1-3	Treatment Emergent Adverse Events Overall and by Cohort- Safety Set		
14.3.1-4	Serious Treatment Emergent Adverse Events Overall and by Cohort- Safety Set		
14.3.1-5	Drug Related Treatment Emergent Adverse Events Overall and by Cohort- Safety Set		
14.3.1-6	Treatment Emergent Adverse Events where Severity Grade>=3, Overall and by Cohort-Safety Set		
14.3.1-7	Treatment Emergent Adverse Events by Severity Grade, Overall – Safety Set		

14.3.2: Lis	sting of Deaths and Other Serious and Significant Adverse Events- Safety Set
14.3.1-1	Listing of Treatment Emergent Adverse Event Leading to Discontinuation or Death- Safety Set
14.3.1-2	Listing of Treatment Emergent Adverse Events Deemed Serious or With a Grade 3 or Above- Safety Set
14.3.4: Ab	onormal Laboratory Value Listing
14.3.4-1	Listing of Abnormal Hematology Results – Safety Set
14.3.4-2	Listing of Abnormal Chemistry Results- Safety Set
14.3.5: Vi	tal Signs
14.3.5-1	Summary and Change from Baseline in Vital Signs- Safety Set
14.3.6: Ot	her Safety Data
14.3.6-1	Summary and Change from Baseline in Hematology Results- Safety Set
14.3.6-2	Summary and Change from Baseline in Chemistry Results- Safety Set
14.3.6-3	Clinical Laboratory Shift Table: Chemistry- Safety Set
14.3.6-4	Clinical Laboratory Shift Table: Hematology- Safety Set
14.3.6-5	Summary and Change from Baseline in ECG Parameters- Safety Set
14.3.6-6	Concomitant Medications- Safety Set
14.3.6-7	Study Drug Exposure- Safety Set
14.4: PK I	Evaluations
14.4-1	Percent of Dose Recovered in Urine per Collection Interval -PK Urine Set
14.4-2	Summary of Urinary Kinetics- PK Urine Set
Listings	
16.2.1-1	Listing of Discontinuations – Consented Population
16.2.2-1	Listing of Protocol Deviations – Safety Set

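### The protocol's pre- to post-dose ECG shift tables are missing from the SAP without declaration, and the separate QT/QTc threshold counts only bound how many subjects newly exceed a limit, mainly at 450

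*SAP*

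**What the plan says.** - **Protocol 12.5.3.4 (ECG).** Besides summary statistics for values and changes, "Shift tables comparing pre- to post-dosing categorical ECG values will be presented" for the safety set. The categories are not defined.
- **Protocol 11.1.4.** "A 12-lead electrocardiogram (ECG) will be taken at two intervals on the day of dosing, including prior to dosing and prior to imaging". Each subject therefore has one simple pair of readings.
- **SAP 8.6 (ECG).** Summary statistics for values and changes from baseline, by visit and cohort. For QT, QTc-Bazett and QTc-Fridericia, "the following groups will be summarized at Baseline and the pre-imaging visit: values above 450, above 480 and above 500". At pre-imaging only, change bands are added: "Increase 31-50, increase >60, decrease 31-60, and decrease >60". No cross-tabulation of baseline against pre-imaging is planned.
- **SAP Table 4.** One ECG table is listed, 14.3.6-5: "Summary and Change from Baseline in ECG Parameters- Safety Set". Shift tables appear for chemistry (14.3.6-3) and hematology (14.3.6-4), in line with SAP 8.4: "A shift table will also be presented showing the shift in values from Baseline to follow up". The listings that can be read include none for ECG.
- **SAP Section 10**, headed "PLANNED TREATMENT SAP CHANGES THAT DIFFER FROM THE PROTOCOL", records several dropped analyses, such as the lesion-count plots and the prior-therapy subgroups. The ECG shift tables are not among them.

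**The concern.** Change from baseline in ECGs is a stated safety endpoint (SAP 3.3). A shift table answers a question about individuals: how many subjects were at or below a limit before dosing and above it afterwards, and how many moved the other way. Separate counts at two times answer a different question, namely how many subjects were above the limit at each time. Subjects who cross upward and subjects who revert offset each other in those counts. The protocol promised the paired display. The SAP keeps it for laboratory data, leaves it out for ECG, and does not say so in the section meant for departures from the protocol.

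**Working it through.** The documents give no QT or QTc rates, so there is no figure of the plan's own to reproduce. The check has four parts.

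**1. The two plans side by side.**

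| ECG output | Protocol 12.5.3.4 | SAP 8.6 and Table 4 |
|---|---|---|
| Values and changes, summary statistics | yes | yes |
| Pre- to post-dose shift table of categories | yes | no |
| Counts above 450, 480, 500 at each time | not mentioned | yes |
| Within-subject change bands | not mentioned | yes, with a gap |
| Omission declared in SAP Section 10 | not applicable | no |

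**2. What two separate counts can tell.** Let N be the subjects with both readings, a the number above a limit at baseline and b the number above it at pre-imaging. Then newly above minus reverted = b - a, and

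max(0, b - a) ≤ newly above ≤ min(b, N - a).

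Take N = 377, the planned number dosed (262 + 115, Protocol 6.2). The values of a and b are assumptions:

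| a | b | Newly above | % of 377 |
|---|---|---|---|
| 0 | 3 | exactly 3 | 0.8 |
| 5 | 5 | 0 to 5 | 0 to 1.3 |
| 20 | 20 | 0 to 20 | 0 to 5.3 |
| 38 | 38 | 0 to 38 | 0 to 10.1 |
| 30 | 40 | 10 to 40 | 2.7 to 10.6 |

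A shift table gives the number directly. The first row shows the exception: with a = 0, every subject above the limit at pre-imaging is new.

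**3. At which limit this matters.** Assume a bivariate normal QTc in ms with the same mean at both times, that is, no drug effect. The total SD is √(between² + within²), and the expected number above limit L is 377 × P(Z > (L - mean)/total SD). For the first scenario, total SD = √(20² + 8²) = 21.5, and at 450 the standardised distance is 35/21.5 = 1.625, which gives 19.6 subjects.

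| Mean, SD between, SD within | Above 450 at each time | of these, new at pre-imaging | Above 480 | Above 500 |
|---|---|---|---|---|
| 415, 20, 8 | 19.6 | 8.3 | 0.5 | 0.01 |
| 420, 20, 10 | 33.9 | 15.2 | 1.4 | 0.07 |
| 420, 22, 12 | 43.6 | 19.7 | 3.1 | 0.27 |

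At 450 the counts are large enough for the range in part 2 to be wide. At 480 it spans a few subjects at most. At 500 the baseline count will usually be zero, and the answer is then exact.

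**4. Whether the change bands fill the gap.**
- 440 to 460 is a rise of 20. It crosses 450 and falls in no band.
- 400 to 440 is a rise of 40. It falls in the 31-50 band and crosses nothing.
- 430 to 485 is a rise of 55. It crosses 450 and 480 and falls in no band, because the increase bands jump from 50 to above 60. The decrease bands (31-60, above 60) have no such gap.

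The bands therefore measure the size of a change, not the crossing of a limit, and one range of increases is not counted.

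**The case against.** A reader might infer that new prolongation cannot be seen at all, or that equal counts would pass as no effect however many subjects were newly prolonged. The documents do not support this. SAP 8.6 also plans paired output: change-from-baseline statistics, which under SAP 5.3 include the minimum and maximum, and within-subject bands. A reader would see the largest individual rise and the number rising by more than 60. The two counts also give a lower and an upper bound, and a zero baseline count removes the ambiguity.

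A reader might also take the 8 to 20 new crossings in the table as missed harm. They are not. The scenarios assume no drug effect, so these crossings are within-subject noise matched by equal reversions, and a net change of zero is then the correct message. In a single-treatment study, a bare count of new crossings would mislead in the other direction. This is why the shift table must show reversions as well.

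Nor do the documents say that the threshold counts were meant to replace the shift tables. The SAP is silent, and the protocol's categories may be normal/abnormal readings rather than QTc limits. If so, the SAP has no shift output for them either.

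Two further points limit the weight. SAP Section 2 treats the table list as a guideline that can be refined without amendment, so absence from Table 4 adds little to the silence of 8.6. And the onsite investigator evaluates each ECG for subject safety (Protocol 11.1.4), so an important finding can also reach the report as an adverse event.

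What remains is the undeclared omission, the missing crossing count at 450, and the gap in the bands. Declaring the omission in Section 10 would settle the first of these only.

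**Conclusion.** The point holds as an undeclared departure from the protocol that loses specific information. The SAP omits the committed ECG shift tables, and its separate counts only bound the number of subjects newly above a limit: 0 to 20 of 377 when both counts are 20. The practical loss is mainly at 450. That ranking of the limits rests on assumed QTc means of 415-420 ms, between-subject SDs of 20-22 and within-subject SDs of 8-12, none of which is in the documents; the bounds themselves need no such assumption. The omission of increases of 51-60 is plain from the SAP's own wording. The output concerned is descriptive safety data, so the primary and secondary efficacy analyses, the error rate and the sample size are untouched. It should be corrected, but it does not threaten the trial's conclusions on efficacy.

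**What to change.** 1. In SAP 8.6 and Table 4, add a baseline by pre-imaging shift table on the safety set for QT, QTc-Bazett and QTc-Fridericia, with categories ≤450, >450-480, >480-500 and >500. Show both the subjects newly above each limit and those who revert, with the number of paired readings as denominator.
2. Give the same table for any other categorical ECG value collected, such as an overall interpretation, since the protocol does not restrict its commitment to QTc.
3. Close the gap in the increase bands so that rises of 51-60 are counted, and state the unit.

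The cost is one descriptive table from readings already collected, plus SAP wording. No new data are needed.

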#### 5.5.4. Change and Percent Change from Baseline

Change from baseline will be computed as any post baseline follow-up value minus the baseline value.

Percent change from baseline will be computed as 100 times the (post-baseline value minus the baseline value) divided by the baseline value. If the baseline value or the post-baseline value is missing, change from baseline and percent change from baseline will be missing.

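### The QT/QTc change bands in SAP 8.6 leave out increases of 51 to 60, so the two increase rows undercount subjects with increases above 30

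*SAP*

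**What the plan says.** SAP 8.6 plans three descriptive views of the ECG data.

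- **Continuous summary.** "Summary statistics for observed and change from baseline values of each ECG parameter will be presented by visit and cohort using the safety set". SAP 5.3 includes the minimum and maximum among the descriptive statistics, and SAP 5.5.4 defines change: "Change from baseline will be computed as any post baseline follow-up value minus the baseline value". An increase is therefore a positive change.
- **Absolute-value groups.** For uncorrected QT and both corrected versions, at baseline and again before imaging, the SAP counts "values above 450, above 480 and above 500".
- **Change bands.** For the same three parameters, before imaging only, the SAP counts four kinds of change: "Increase 31-50, increase >60, decrease 31-60, and decrease >60".

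No unit is given for the cut-offs.

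Protocol 12.5.3.4 also plans pre- versus post-dose shift tables for categorical ECG results in the safety set, but defines no categories and no change bands. The only ECG output in SAP Table 4, as shown, is Table 14.3.6-5, "Summary and Change from Baseline in ECG Parameters- Safety Set". SAP section 10, which lists departures from the protocol, says nothing on this point.

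**The concern.** In each direction the four bands should split all changes larger than 30 into a moderate group and a large group. They do so for decreases. For increases, the moderate group stops at 50 and the large group starts above 60, so the interval between them belongs to neither.

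Change from baseline in ECGs is a safety endpoint in SAP 3.3, and pre- and post-imaging ECGs come under the safety secondary endpoint in Protocol 5.2. The gap lies on the prolongation side. A reader who adds the two increase rows to find how many subjects had an increase above 30 would get too small a number, and nothing in the table would show it. The schedule of assessments has one post-dose ECG per subject, taken before imaging, so a subject who is missed there has no later scheduled ECG at which to be counted.

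**Working it through.** **Step 1: coverage of the bands.** The plan has no figure to reproduce here. The check takes every whole-unit change *d* from -100 to +100 and asks which band of SAP 8.6 contains it.

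| Change *d* | Band as written | Band if the first increase band is 31-60 |
|---|---|---|
| below -60 | decrease >60 | decrease >60 |
| -60 to -31 | decrease 31-60 | decrease 31-60 |
| 31 to 50 | increase 31-50 | increase 31-60 |
| **51 to 60** | **none** | increase 31-60 |
| above 60 | increase >60 | increase >60 |

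As written, the ten values 51, 52, ..., 60 are the only changes larger than 30 in size that fall in no band. No value falls in two bands. With the upper limit at 60, every change larger than 30 is covered, again without overlap.

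**Step 2: whether another part of the plan fills the gap.** Protocol 12.5.3.4 gives no change bands, SAP section 10 mentions none, and no other section supplies a 51-60 increase band.

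The absolute-value groups answer a different question. As an illustration, a rise from 380 to 438 is a change of 438 - 380 = +58. It falls in no change band, and 438 is not above 450, so it falls in no absolute group either. A rise from 400 to 458 is also +58. It falls in no change band but is counted above 450.

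**Step 3: rough size.** Inputs:

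- *N* = 377, the approximate planned number dosed in both cohorts (Protocol 6.2). The number with paired ECGs could be smaller.
- Change normally distributed with mean 0 and SD 15 or 20. This is an assumption; the documents give no SD for QT or QTc change.
- Whole-unit recording, so 51 to 60 corresponds to 50.5 to 60.5.

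Expected number in the gap, per parameter: *N* × [P(Z > 50.5/SD) - P(Z > 60.5/SD)].

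- SD 20: 377 × [P(Z > 2.525) - P(Z > 3.025)] = 377 × (0.00578 - 0.00124) = 377 × 0.00454 ≈ **1.7**.
- SD 15: 377 × [P(Z > 3.367) - P(Z > 4.033)] = 377 × (0.000380 - 0.000027) = 377 × 0.000353 ≈ **0.1**.

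For scale, the expected number with any increase above 30 is *N* × P(Z > 30.5/SD). At SD 20 this is 377 × 0.0636 ≈ 24.0, and at SD 15 it is 377 × 0.0210 ≈ 7.9. The undercount is then about 1.7/24.0 ≈ 7% and 0.13/7.9 ≈ 2% of those subjects.

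**The case against.** The strongest reply is that little is lost.

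- **These subjects are still in the output.** A +58 change enters the continuous change statistics, and it is printed as the maximum if it is the largest in its cohort. The absolute-value groups count the subject when the value is high enough. Under Protocol 11.1.4 the site investigator evaluates each ECG for safety and reports adverse events. All of this stands. A reader might infer that such subjects disappear from the ECG table altogether, and the documents do not support that: they are missing from the change bands only. What the reply does not restore is the count. A maximum shows at most one value per cohort, the absolute groups do not measure change, and Table 4 as shown has no by-subject ECG listing.
- **It is a typing error.** Probably so. The same sentence uses 31-60 for decreases and misspells Fridericia. A misread digit in the PDF text cannot be excluded from the text alone, though nothing positively shows one. Because the gap is on the prolongation side, a reader might also infer that the bands were drawn to make the drug look safer. Nothing in the documents supports that: the top increase band is intact, and no rationale for the asymmetry appears anywhere.
- **The numbers are small and assumed.** This also stands. No test, confidence interval or success criterion uses these bands.
- **Shells may be refined without an amendment.** SAP section 2 allows this for tables, listings and their shells. The band is printed in the body of the SAP, however, so a programmer who follows that text would reproduce the gap.

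**Conclusion.** The point holds in a limited form. As printed, increases of 51 to 60 in QT, QTc-Bazett and QTc-Fridericia fall in no change band, while decreases of the same size are counted. The two increase rows therefore undercount increases above 30. That follows from the text alone and needs no assumption, apart from reading the unstated unit as ms.

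The size does rest on assumptions. With mean change 0, SD 15 to 20 and 377 subjects, about 0.1 to 1.7 subjects per parameter are affected; a different SD would change this. The consequence is an incomplete descriptive safety table. No efficacy analysis, primary or secondary, is touched. It is still worth correcting, because categorical QT tables exist to show a few outlying subjects, and one or two omitted subjects can matter in such a row.

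**What to change.** In SAP 8.6, change the upper limit of the first increase band from 50 to 60, so that it reads 31-60 for QT, QTc-Bazett and QTc-Fridericia. Make the same change in the shell for Table 14.3.6-5. The increase bands then meet at 60 and mirror the decrease bands. State the unit at the same time.

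The cost is one number in the SAP text and one in the shell. No new data or analysis is needed, provided the correction is made before the table is programmed.
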